### 4.0 STUDY POPULATION

As described above, this study defines the obstetrical surgeons as “users” and the patients in whom the drain is placed as “participants.” The participants consist of women undergoing planned CD for reasons unrelated to this study. We expect to enroll five (5) obstetrical surgeons of various levels of experience who will each place a drain in one to three participants for a total of 10 participants who are qualified based on the Instructions for Use (IFU) *and* who consent to participation. The following contraindications serve as exclusion criteria.

- Known intrauterine or cervical pathology that would interfere with device placement and/or use
- Ongoing intrauterine pregnancy
- Untreated uterine rupture
- Unresolved uterine inversion
- Current cervical cancer
- Current purulent infection of vagina, cervix, or uterus
- Retained products of conception
- Arterial bleeding requiring surgical or angiographic embolization
- Indication for hysterectomy
- Lack of study consent.

## 5.0 DEVICE DESCRIPTION

The *DAISY* device consists of a soft silicone drainage tube (proximal end) attached to a semi-flexible catheter, inserted through the hysterotomy created at the time of the CD after the uterus is evacuated of products of conception. **(Figure 1)**..

Figure 1

The Drain is threaded through the cervix and the semi-flexible catheter traverses out the vagina where it attaches to suction tubing attached to a canister. **(Figure 2)**

[figure not shown]

Figure 2

The Drain will be placed on continuous suction according to the IFU for the first two postpartum hours or more if required following evaluation of uterine tone. The drain utilizes standard suction tubing and either wall or portable suction, all readily available on labor and delivery units. The Drain is a closed system that allows clinicians to quantify blood loss and permits direct visual determination of efficacy as evidenced by definitive contraction of the uterus after the uterine incision is repaired.

The *DAISY* drain will be placed intraoperatively after delivery of the placenta, stabilization of the patient, and cleansing of the uterine cavity but prior to closure of the hysterotomy. The *DAISY* drain will be placed through the hysterotomy and threaded through the cervix and vaginal canal, out the introitus, so the distal end is accessible outside of the body (Figure 3).

[figure not shown]

Figure 3

The hysterotomy is then closed taking care not to loop any sutures around the drain. Blood flow through the lumen will be measured by attaching the suction tubing to a fluid collection container (e.g., bag, or calibrated suction canister). Tubing must be secured to the thighs using a foley catheter securing adhesive to avoid displacement before attaching to the suction canister. For this Protocol, 100mmHg of suction is recommended to induce uterine involution. The *DAISY* drain will remain in place for a minimum of 3 hours while the Participant is in the recovery unit. At the end of 2-hours, the uterus will be evaluated by manual palpation and abdominal ultrasound. The abdominal ultrasound will be performed to document device placement and to assess uterine involution, approximate uterine size and uterine cavity size, presence of intrauterine clots or retained products of conception. Following the ultrasound, the suction is to be reduced to 10mmHg for 5 minutes. After 5 minutes, the investigator will again assess uterine tone and perform another ultrasound. After the second ultrasound, the Daisy is left in place with the suction at 10mmHg for 30 minutes. After 30 minutes, the investigator is to again assess uterine tone manually and perform the third ultrasound.

NOTE: If the uterine cavity is assessed by ultrasound and/or clinically determined to contain clots or products of conception, the device will be removed after discontinuation of suction, the study participant discontinued, and management undertaken per institutional protocol. Thirty minutes before device removal, any suction applied must be discontinued to observe for any additional bleeding. Clinical management of the subject will determine the time for device removal, but the device must be removed within 24 hours of placement. [See “Instructions for Use” provided to the user.]

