#### **DAISY DRAIN Removal:**

The user who has undergone IFU training will remove the *DAISY* drain after at least two hours post CD based on clinical management. Suction will be discontinued, and the participant observed for 30 minutes before removal. One method of determining if the *DAISY* drain is no longer needed is by checking and documenting uterine tone. If uterine tone has returned to normal as assessed by palpation, the *DAISY* drain may be removed. (Note: If the uterine tone has not returned to normal, the user may choose to leave the drain in place and resume suction.) Upon drain removal, suction is briefly reapplied to collect any blood in the lumen after the 30-minute resting period. **Suction must be discontinued before the drain is removed.** Placing one hand on the abdomen to support the uterus while the other hand slowly withdraws the drain, the person removing the drain will evaluate the ease of drain removal. [See “Instructions for Use” provided to the user.]

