## RISK & RISK MITIGATION

The following risks have been identified as “potential” based on similar devices:

- Perforation: The risk of perforation is mitigated by the placement of this drain under direct observation followed by an ultrasound confirming correct placement after closure. In addition, the drain is constructed of smooth, atraumatic materials.
- Endometritis: Endometritis is mitigated by selection of appropriate materials, selection of appropriate participants, and limited drain dwelling time. Endometritis can occur regardless of device use. To evaluate the occurrence of endometritis, participants will be followed out to the time of the post-partum visit.
- Vaginitis or tissue trauma: Vaginitis or tissue trauma is mitigated by using non-irritating materials and an atraumatic drain design. To evaluate for the occurrence of vaginitis or tissue trauma, participants will be followed out to the time of the post-partum visit.
- Infection: Infection is mitigated through the direction of drain placement, sterility of the drain, and limited time of exposure to the drain (~2.5 hours) in addition to careful participant selection.
- Loss of Participant Confidentiality: The principal risk of a signed consent document would be the potential harm resulting from a breach of confidentiality. Every precaution will be taken to minimize this. The original signed consent documents will be stored in the research office which will be locked when not attended. Electronic logs will be stored in password protected desktop computers, accessible only to the research team. Data will

be stored according to institutional policy. At any given time, there will be 1 to 3 people from the Sponsor and/or site's research team present to abstract data. De-identified data will be collected in the database which will be accessible to outside institution team members. Data transferred out of the site will be de-identified data with the study ID number. The key containing the study ID number with the participant information will be accessible to the study team only and will be stored securely on password-protected computers. No genetic information will be collected for this study.

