**NOTE:** Participation in the study is not expected to alter the likelihood of occurrence or severity of any standard surgical risks at the time of the CD. There is no risk to the fetus since the drain is placed after birth. Other than drain placement/removal and addition of suction during placement, there are no changes to the standard operative procedures. Participants are unlikely to experience sensation of the drain placement because it will be placed and removed while the participant is still under the influence of the epidural or spinal anesthesia. There is a small risk of unintentional loss of confidentiality. All efforts will be made to minimize this risk. There are no anticipated emotional, psychological, economic, legal, or social risks to the participants associated with this study.

For these reasons, it is the opinion of the Sponsor that this study design poses no significant risk to the participant.

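### Sections 5.0 and 7.0 give incompatible drain times (3 hours, two hours, about 2.5 hours), so the three planned assessments may not all be done as specified and the stated exposure is too short

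*Protocol*

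**What the plan says.** Drain time is stated in three places in the protocol.

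- **Section 5.0, Device Description.** The "drain will remain in place for a minimum of 3 hours while the Participant is in the recovery unit". The sequence starts with "At the end of 2-hours, the uterus will be evaluated by manual palpation and abdominal ultrasound". Suction then drops to 10 mmHg for 5 minutes before a second tone check and ultrasound, and stays at 10 mmHg for another 30 minutes before a third. Any suction must be off for the 30 minutes before removal. There is also a ceiling: "the device must be removed within 24 hours of placement".
- **Section 5.0, DAISY Drain Removal.** The trained user removes the "drain after at least two hours post CD based on clinical management", after 30 minutes of observation with suction off. Normal tone on palpation is enough to allow removal. This text mentions neither the 3-hour minimum nor the three assessments.
- **Section 7.0, Risk & Risk Mitigation.** Infection is said to be mitigated in part by "limited time of exposure to the drain (~2.5 hours". The note that follows says of the drain that "it will be placed and removed while the participant is still under the influence of the epidural or spinal anesthesia".

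On suction, Section 5.0 also provides for "continuous suction according to the IFU for the first two postpartum hours or more if required following evaluation of uterine tone". The step to 10 mmHg after the first ultrasound carries no tone condition.

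Appendix 2 lists uterine tone, the postpartum ultrasound scale and the ultrasound evaluations at three time points each. Suction level is listed without time points.

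**The concern.** One procedure has two different minimum drain times, and the risk section quotes a third figure that is below the larger minimum and below the total of the protocol's own steps.

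Two things are at stake. The first is the data. Section 3.0 names the effects of adding suction as something the sponsor wants to learn, and the three assessments are the planned participant-level observations of uterine tone and size as suction is stepped down. With 10 participants, each one not fully observed is a tenth of the sample. If continuous suction is extended in some participants and stepped down in others, the second and third assessments are made under different conditions, and the data list does not ensure that this can be seen.

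The second is the risk statement. Section 7.0 presents its mitigations as support for the non-significant-risk determination. An ethics board reading about 2.5 hours is reading a figure that a participant who completes Section 5.0 will exceed.

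**Working it through.** **Inputs**, all from Section 5.0 unless noted: suction before the first assessment, 120 min; first step at 10 mmHg, 5 min; second step at 10 mmHg, 30 min; suction off before removal, 30 min; stated minimum, 180 min; minimum in the removal text, 120 min; exposure in Section 7.0, about 150 min. The protocol gives no duration for an ultrasound, so I assume 0, 5 or 10 min each. All times are first put on one clock.

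**1. Can the stated 2.5 hours be reproduced?** Only by leaving out required steps.

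- 120 + 30 (suction off) = 150 min, which omits both 10 mmHg steps.
- 120 + 5 + 30 = 155 min, which is close but omits the suction-off period.

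**2. Time needed by the full sequence.**

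- Assessment 1: 120 min (2 h 00).
- Assessment 2: 120 + 5 = 125 min (2 h 05).
- Assessment 3: 125 + 30 = 155 min (2 h 35).
- Earliest removal: 155 + 30 = 185 min (3 h 05).

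Three ultrasounds of u minutes each make the earliest removal 185 + 3u.

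| u (min, assumed) | Earliest removal | Excess over 150 min | Excess over 180 min |
|---|---|---|---|
| 0 | 3 h 05 | 35 | 5 |
| 5 | 3 h 20 | 50 | 20 |
| 10 | 3 h 35 | 65 | 35 |

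The Section 7.0 figure is also 180 − 150 = 30 min below the minimum stated in Section 5.0.

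**3. What each removal time leaves of the assessments (u = 0).**

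| Removal at | Suction off by | Assessments reached | Reached with suction still on |
|---|---|---|---|
| 2 h 00 (removal text, literal) | 1 h 30 | 1 of 3 | 0 |
| 2 h 30 (two hours of suction, then the rest) | 2 h 00 | 2 of 3 | 1 |
| 3 h 00 (stated minimum) | 2 h 30 | 3 of 3 | 2 |

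At 2 h 00, suction would stop at 120 − 30 = 90 min, short of two hours of continuous suction, and assessments 2 and 3 are lost. At 2 h 30, assessment 3 is lost, and assessment 2 falls in the suction-off period instead of at 10 mmHg. On neither reading can all three be done as specified. At exactly 3 h 00, suction goes off 5 min before assessment 3 is due at 10 mmHg.

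**4. Do the different clocks explain the gap?** The removal text counts from the cesarean. The 3-hour minimum is tied to the recovery unit, the suction period is counted postpartum, and the 24-hour limit runs from placement. For the two minimums to coincide, the post-cesarean clock would have to start 180 − 120 = 60 min after the 3-hour clock. If the 3 hours are counted in recovery, that clock starts after surgery and the gap does not shrink. If they are counted from placement, the gap shrinks by the time left in surgery, which the protocol does not give.

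**5. Suction level.** Read together, the two suction statements allow one participant to remain on extended continuous suction (100 mmHg is the recommended level) after the first assessment while another is at 10 mmHg. A single suction-level item in Appendix 2 need not show which.

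**The case against.** The best defence is that both drain times are floors. A user who waits out the longer one satisfies both. Section 5.0 words the three assessments as required steps, and the removal text does not waive them. The Instructions for Use are not shown and may set out the sequence. The study looks mainly at users, and Section 8.0 describes analysis of questionnaire responses only, with no hypothesis on the step-down data. The 2.5 hours is marked approximate and is one infection mitigation among several.

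Part of this stands. A careful user can comply with everything, and no formal comparison is at risk. But the removal text permits removal without mentioning the assessments or the longer minimum, and an unseen instruction sheet does not repair contradictory protocol text. An approximate figure covers a 5-minute difference; it does not cover 30 to 65 minutes.

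Several stronger readings are tempting and are not supported:

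- **Every drain and suction time conflicts.** Two hours of suction or more is compatible with a 3-hour minimum, and a 24-hour ceiling contradicts no minimum. Dividing that ceiling by 2.5 hours measures no error.
- **Two of the three assessments will be lost.** That is the worst case, with the removal text read alone.
- **Resuming suction disturbs the second and third assessments.** In the removal text, resumption follows the pre-removal rest, which in the full sequence comes after the third assessment. Only the provision for extended continuous suction can alter the earlier time points.
- **The procedure outlasts the anesthesia.** The protocol gives no duration of block, so this cannot be shown for a removal at about 3 hours.
- **Missing assessments will be informative.** Removal conditional on normal tone makes this plausible, but the protocol offers nothing to establish it.

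**Conclusion.** The point holds as an internal inconsistency: the text is wrong as written and should be fixed. The conflict is between the 3-hour minimum and its step sequence, the two-hour removal text, and the 2.5-hour exposure in Section 7.0. The exposure is understated by 30 min against the stated minimum and by 35 min against the step total, or up to 65 min if each ultrasound takes 10 min. A user who follows the removal text could miss one assessment (removal at 2 h 30) or two (removal at 2 h 00). The lack of a tone condition on the step-down, with suction level not listed by time point, is a smaller, related defect.

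The sizes rest on a common clock and on assumed scan times of 0 to 10 min. A reader might go further and infer that the non-significant-risk determination fails. The documents do not support that: dwell time is one of several grounds, and Section 7.0 also relies on sterility, direction of placement, participant selection and the device's exempt status. No view is taken on which of the stated times is right.

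**What to change.** - The sponsor and clinical team should reconcile the device-description and removal text of Section 5.0 into one timeline with one clock origin. It should cover how an extension of continuous suction fits with the step to 10 mmHg.
- State whether the three assessments must be complete before elective removal.
- Restate the exposure in Section 7.0 as the minimum and maximum that follow from that timeline, and check the statement about removal under anesthesia against it.
- In Appendix 2, record suction level at each of the three assessments, and the reason for any assessment not done.

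The cost is protocol wording and a few case report form fields, with ethics board review of the amendment. Any participant-facing text that quotes the exposure would need to match; the consent form was not available to check. The exposure stated in Section 7.0 may become less favourable. Sample size and the questionnaire analysis are unaffected.

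### Protocol section 5.0 lowers suction to 10 mmHg after the 2-hour check whatever the uterine tone, although the same section extends suction when tone requires it

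*Protocol*

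**What the plan says.** All the relevant text is in Protocol section 5.0.

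- **Device description (after Figure 2).** The drain is on "continuous suction according to the IFU for the first two postpartum hours or more if required following evaluation of uterine tone". The length of suction therefore depends on a tone evaluation.
- **Working level (after Figure 3).** "For this Protocol, 100mmHg of suction is recommended to induce uterine involution".
- **First evaluation.** "At the end of 2-hours, the uterus will be evaluated by manual palpation and abdominal ultrasound".
- **First step-down.** "Following the ultrasound, the suction is to be reduced to 10mmHg for 5 minutes". Tone and ultrasound are then repeated.
- **Second low-suction period.** "After the second ultrasound, the Daisy is left in place with the suction at 10mmHg for 30 minutes". Tone and ultrasound are then assessed a third time.
- **Written exit.** If the cavity is seen on ultrasound or "clinically determined to contain clots or products of conception, the device will be removed after discontinuation of suction", the participant is discontinued and managed by institutional protocol.
- **Removal.** "Suction will be discontinued, and the participant observed for 30 minutes before removal". If tone is not normal at that stage, "the user may choose to leave the drain in place and resume suction".

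**The concern.** The evaluation that the device description uses to decide whether suction goes on is the one that the schedule follows with a reduction, whatever it shows. A user who finds inadequate tone at 2 hours can keep the working level, as the device description allows, and depart from the schedule. Or the user can follow the schedule and set the extension aside. The investigator is required to follow the protocol and explain deviations (section 10.0), so the user should not have to choose.

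The case is foreseeable. The Summary limits participants to women not in active labor, and section 2.0 describes atony after cesarean delivery as relatively common in the non-laboring patient. Suction is also the one off-label element of the study (section 7.0), and section 3.0 lists its effects among the things the Sponsor wants to learn.

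Two things are at stake. One is bedside management of a woman whose uterus is not contracting well. The other is whether the second and third readings are taken at the same suction level in all ten participants.

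**Working it through.** The protocol states no figure for this point, so the check compares the text and adds the stated durations.

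**Step 1. Timeline from the 2-hour evaluation, scan time ignored**

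| Minutes after 2 h | Event | Suction afterwards | Action tied to tone in the schedule |
|---|---|---|---|
| 0 | Reading 1: tone and ultrasound | 10 mmHg | none |
| 5 | Reading 2: tone and ultrasound | 10 mmHg | none |
| 5 + 30 = 35 | Reading 3: tone and ultrasound | not fixed | none |

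Time at reduced suction is 5 + 30 = 35 minutes, from 2 h 00 to 2 h 35. This is a minimum, because the second ultrasound takes time that is not stated.

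**Step 2. Size of the reduction**

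10 / 100 = 10% of the recommended level.

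**Step 3. Does any other provision suspend the step-down for poor tone?**

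- The exit for clots or products of conception does not cover poor tone with an empty cavity.
- The option to resume suction is in the removal paragraph, after the instruction to turn suction off. It does not act at reading 1 or reading 2.
- Clinical management, as section 5.0 uses it, sets the time of removal, not the suction level during the schedule.
- The extension clause in the device description does speak to poor tone, but the schedule neither repeats it nor refers to it.

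**Step 4. Could 10 mmHg count as the extended continuous suction?**

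In wording, perhaps, since 10 mmHg is still suction. But the extension is prompted by tone, and 100 mmHg is the level named for producing involution. An extension because of poor tone most naturally means the working level.

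The schedule thus has no slot for continued working-level suction after the 2-hour evaluation, and none of its three tone readings has a tone-based action.

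**The case against.** The strongest reply is that section 5.0 should be read as a whole: the device description gives the rule with its tone-based extension, and the schedule gives the ordinary case. That reading is possible and may be what the Sponsor intends. But the schedule does not say so, and its instruction to reduce suction is worded without condition.

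A second reply is that suction is applied according to the IFU, which is not shown and may hold a tone rule. This stands as a limit on severity. It does not reconcile the two paragraphs, and section 3.0 makes the accuracy of the IFU one of the things under test.

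A third is that standard care continues (section 6.0, Alternatives to Participation), so uterotonics and other measures stay available. This also stands and limits the consequence.

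A fourth is that a uniform step-down gives comparable readings in every woman. That is a real advantage, and the reason to keep the step-down as the default.

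Two stronger readings are tempting, and the documents do not support them.

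- **A 65-minute delay.** A reader might add the 30-minute suction-off observation to the 35 minutes (35 + 30 = 65, ending at 3 h 05). But nothing sends a woman with poor tone into the removal sequence. Removal timing is by clinical management, up to 24 hours after placement, and the option to resume suction is not stated to wait for the full 30 minutes.
- **An error in Appendix 2.** A reader might infer that, because the suction-level item has no time points while tone and ultrasound have three, only one level is recorded. Appendix 2 is a list of items and the case report form is not shown. On the default schedule the levels at readings 2 and 3 are already known to be 10 mmHg.

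**Conclusion.** The conflict is real and minor. Followed literally, the schedule lowers suction to a tenth of the recommended level, for at least 35 minutes, in a woman whose tone is inadequate. The device description in the same section would let suction continue.

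This rests on two assumptions: that the extension means the working level rather than 10 mmHg, and that the IFU does not already settle the matter. The number of women affected is unknown, because the protocol gives no frequency of inadequate tone at 2 hours.

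The only analysis stated in section 8.0, of questionnaire scores, does not change, and section 6.0 places the study's focus more on users than on participants. The reason to act is clarity in a bedside instruction and, second, knowing the suction level behind each tone and ultrasound reading.

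**What to change.** Keep the step-down as the default and add to the schedule in section 5.0:

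*If uterine tone is inadequate at the 2-hour evaluation, or is lost at the 5-minute or 30-minute reading, suction is kept at or returned to 100 mmHg (or as the IFU states) and clinical management applies; remaining tone and ultrasound readings are still taken at their scheduled times, with the suction level at each reading recorded.*

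The rule for clots and products of conception and the 24-hour limit stay as they are. No endpoint, procedure, visit or participant is added.

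The cost is that a few women may have no reading at 10 mmHg. Those readings will then describe mainly women with adequate tone, and the report should say so.
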